#### **13.1.4. NORMALITY AND HOMOGENEITY OF PRIMARY EFFICACY VARIABLE**

The residuals from the primary efficacy ANCOVA as well as the sensitivity analysis MMRM are to be checked for normality and homogeneity of variance. Normality is to be examined by normal probability plots, while homogeneity of variance will be assessed by plotting the residuals against the predicted values for the model. Any deviation from either assumption may result in further analysis using non parametric analysis of the primary efficacy variable or using an appropriate alternative transformation (such as logarithmic or power transformation) of the data.

## **13.2. SECONDARY EFFICACY**

### **13.2.1. SECONDARY EFFICACY VARIABLES & DERIVATIONS**

#### **13.2.1.1. Mean Total Rhinoconjunctivitis Symptom Score (TRSS)**

The daily TRSS is to be derived as described in [Section 13.1.1: Primary Efficacy Variable & Derivation](#).

The mean of the daily TRSS for each annual Allergy Assessment Period is to be calculated over all days with complete data.

#### **13.2.1.2. Mean Component Scores of Total Rhinoconjunctivitis Symptom Score (TRSS)**

The TRSS consists of two components:

- Total Nasal Symptom Score (TNSS)

The TNSS is the sum of four individual nasal symptoms: runny nose, sneezing, blocked nose, and itchy nose. The TNSS will have a range of 0 to 12. The TNSS is to be calculated on each day as follows:

---

Document: CP007A SAP.docx

Author: [name]

Version Number:

V 2.0

Version Date:

23 Feb 2017

Template No: CS\_TP\_BS016 – Revision 3

Reference: CS\_WI\_BS005

Effective Date: 01May2012

Copyright © 2012 Quintiles Transnational Corp. All rights reserved.

The contents of this document are confidential and proprietary to Quintiles Transnational Corp. Unauthorized use, disclosure or reproduction is strictly prohibited.

TNSS = Runny Nose + Sneezing + Blocked Nose + Itchy Nose.

Mean TNSS is to be calculated for each annual Allergy Assessment Period over all days with complete data.

- Total Ocular Symptom Score (TOSS)

The TOSS is the sum of four individual ocular symptoms: itchy eyes, watery eyes, red eyes and sore eyes. The TOSS will have a range of 0 to 12. The TOSS is to be calculated on each day as follows:

TOSS = Itchy Eyes + Watery Eyes + Red Eyes + Sore Eyes.

Mean TOSS is to be calculated for each annual Allergy Assessment Period over all days with complete data.

#### 13.2.1.3. Rescue Allergy Medication Score (RMS)

The daily RMS is to be derived as described in [Section 13.1.1: Primary Efficacy Variable & Derivation](#). The mean of the daily RMS for each annual Allergy Assessment Period is to be calculated over all days with complete data.

#### 13.2.1.4. Mean Rhinoconjunctivitis Quality of Life Questionnaire (RQLQ) Score

The self-administered RQLQ with Standardised Activities for 12 years and older (RQLQ(S)  $\geq 12$ ) is to be used in this study.

The RQLQ will be completed as a once off assessment at the end of the annual Allergy Assessment Period.

The RQLQ has 28 questions in seven domains (activities, sleep, non-nose/eye symptoms, practical problems, nasal symptoms, eye symptoms, and emotional). Refer to [APPENDIX 2: Complete Questionnaires](#), for the complete questionnaire. For each question subjects record how troubled they have been during the last week on a 7-point scale. For all domains, except Emotional, the scores are (0 = Not troubled to 6 = Extremely troubled). For the Emotional domain the 7-point scale is (0 = None of the Time to 6 = All of the Time). The overall RQLQ score is the mean of all 28 responses and the individual domain scores are the means of the items within those domains.

The domains are defined as follows:

- Activities: Questions 1 to 3
- Sleep: Questions 4 to 6
- Non-nose/eye symptoms: Questions 7 to 13

---

Document: CP007A SAP.docx

Author: [name]

Version Number:

V 2.0

Version Date:

23 Feb 2017

Template No: CS\_TP\_BS016 – Revision 3

Reference: CS\_WI\_BS005

Effective Date: 01May2012

Copyright © 2012 Quintiles Transnational Corp. All rights reserved.

The contents of this document are confidential and proprietary to Quintiles Transnational Corp. Unauthorized use, disclosure or reproduction is strictly prohibited.

- Practical problems: Questions 14 to 16
- Nasal symptoms: Questions 17 to 20
- Eye symptoms: Questions 21 to 24
- Emotional: Questions 25 to 28

#### 13.2.1.5. Asthma evaluations

- Mean Asthma Symptom Score (ASS)

The ASS has six questions which are answered daily by the subject for each annual Allergy Assessment Period. All subjects are to indicate how they have been in the past 24 hours with regards to:

- Coughing
- Wheezing
- Shortness of breath

In addition, for subjects with asthma only, the ASS is to include the following questions:

- Limitation of activities
- Nocturnal symptoms or awakenings due to asthma
- Need for short-acting inhaled  $\beta_2$ agonist treatment

There is a four point scale (0 to 3) for each question. For cough, wheezing and shortness of breath symptoms the subject will rate the severity as follows:

0 = absent

1 = mild, barely noticeable

2 = moderate, annoying/troublesome

3 = severe, very annoying/ very troublesome

For limitations of activities the subject will rate the severity as follows:

0 = not limited

1 = very slightly limited

---

Document: CP007A SAP.docx

Author: [name]

Version Number:

V 2.0

Version Date:

23 Feb 2017

Template No: CS\_TP\_BS016 – Revision 3

Reference: CS\_WI\_BS005

Effective Date: 01May2012

Copyright © 2012 Quintiles Transnational Corp. All rights reserved.

The contents of this document are confidential and proprietary to Quintiles Transnational Corp. Unauthorized use, disclosure or reproduction is strictly prohibited.

2 = slightly limited

3 = moderately limited or worse

For nocturnal symptoms or awakenings due to asthma the subject will rate how asthma has affected them overnight (last night) as follows:

0 = not at all

1 = hardly at all

2 = a few minutes disturbance

3 = several times or more

For use of short-acting inhaled  $\beta_2$  agonist treatments the subjects will record how many puffs of reliever medication (e.g. albuterol or salbutamol) they have used as follows:

0 = none

1 = one

2 = two

3 = three or more

The questions are equally weighted and the ASS for each day is to be calculated as the mean of the six relevant questions (for subjects with asthma) or the mean of the three relevant questions (for all other subjects (including subjects with asthma)) separately. For the analysis of all subjects (including subjects with asthma) only the symptoms coughing, wheezing and shortness of breath are to be used in the calculation of the ASS.

The mean of the daily ASS for each annual Allergy Assessment Period is to be calculated over all days with complete data.

Subjects are to be classified as having asthma based on the subjects Asthma Progression eDiary response to the question, 'Are you diagnosed with asthma?'. The response to the last monthly assessment prior to each year's annual allergy assessment is to be used to classify subjects as either asthmatic (response of 'Yes') or non-asthmatic (response of 'No').

- Asthma onset and progression

On a monthly basis subjects will enter in their diary binders the following three questions related to asthma onset and progression:

- o Are you diagnosed with asthma
- o If yes, has your doctor prescribed stronger medicine
- o Have your symptoms have been significantly worse in the last month

Additionally, at the start of each annual Allergy Assessment Period subjects will indicate whether

---

Document: CP007A SAP.docx

Author: [name]

Version Number:

V 2.0

Version Date:

23 Feb 2017

Template No: CS\_TP\_BS016 – Revision 3

Reference: CS\_WI\_BS005

Effective Date: 01May2012

Copyright © 2012 Quintiles Transnational Corp. All rights reserved.

The contents of this document are confidential and proprietary to Quintiles Transnational Corp. Unauthorized use, disclosure or reproduction is strictly prohibited.

they have been diagnosed with asthma during the last year.

### 13.2.2. ANALYSIS OF SECONDARY EFFICACY VARIABLES

The secondary efficacy analysis is to be performed for the FAS.

#### 13.2.2.1. Mean Total Rhinoconjunctivitis Symptom Score (TRSS)

The LS mean difference in mean TRSS between treatment arms, along with 95% two-sided CIs and p-value are to be estimated using the same ANCOVA as for the primary efficacy variable as described in [Section 13.1.2: Primary Analysis of Primary Efficacy Variable](#) and presented in a similar manner, excluding the ratio of LS means and 95% Fieller's CI.

Additionally, the LS mean and 95% CI for the TRSS at the CP007 study endpoint of PAC3 is to be calculated for the CP007A FAS subjects using the same ANCOVA. The LS mean and 95% CI is to be presented by treatment arm.

The TRSS analysis is not to utilize the Bonferroni-Holm procedure to assess each of the two treatment comparisons (two courses of Cat-PAD vs. Placebo and one course of Cat-PAD vs. Placebo). Each treatment comparison p-value is to be tested at the 0.05 alpha level.

Observed and change from Baseline values are to be summarised by descriptive statistics (n, mean, SD, median, minimum and maximum) for each annual Allergy Assessment Period and treatment arm.

The analyses are to be repeated for the mITT population.

#### 13.2.2.2. Mean Component Scores of Total Rhinoconjunctivitis Symptom Score (TRSS)

The LS mean difference in mean TOSS and TNSS between treatment arms, along with 95% two-sided CIs and p-value are to be estimated using the same ANCOVA as for the primary efficacy variable as described in [Section 13.1.2: Primary Analysis of Primary Efficacy Variable](#) and presented in a similar manner, excluding the ratio of LS means and 95% Fieller's CI.

Additionally, the LS mean and 95% CI for the TOSS and TNSS at the CP007 study endpoint of PAC3 is to be calculated for the CP007A FAS subjects using the same ANCOVA. The LS mean and 95% CI is to be presented by treatment arm.

The TOSS and TNSS analyses are not to utilize the Bonferroni-Holm procedure to assess each of the two treatment comparisons (two courses of Cat-PAD vs. Placebo and one course of Cat-PAD vs. Placebo). Each treatment comparison p-value is to be tested at the 0.05 alpha level.

Observed and change from Baseline values are to be summarised by descriptive statistics (n,

---

Document: CP007A SAP.docx

Author: [name]

Version Number:

V 2.0

Version Date:

23 Feb 2017

Template No: CS\_TP\_BS016 – Revision 3

Reference: CS\_WI\_BS005

Effective Date: 01May2012

Copyright © 2012 Quintiles Transnational Corp. All rights reserved.

The contents of this document are confidential and proprietary to Quintiles Transnational Corp. Unauthorized use, disclosure or reproduction is strictly prohibited.

mean, SD, median, minimum and maximum) for each annual Allergy Assessment Period and treatment arm.

The analyses are to be repeated for the mITT population.

#### 13.2.2.3. Rescue Allergy Medication Score (RMS)

The LS mean difference in mean RMS between treatment arms, along with 95% two-sided CIs and p-value are to be estimated using the same ANCOVA as for the primary efficacy variable as described in [Section 13.1.2: Primary Analysis of Primary Efficacy Variable](#) and presented in a similar manner, excluding the ratio of LS means and 95% Fieller's CI.

Additionally, the LS mean and 95% CI for the RMS at the CP007 study endpoint of PAC3 is to be calculated for the CP007A FAS subjects using the same ANCOVA. The LS mean and 95% CI is to be presented by treatment arm.

The RMS analysis is not to utilize the Bonferroni-Holm procedure to assess each of the two treatment comparisons (two courses of Cat-PAD vs. Placebo and one course of Cat-PAD vs. Placebo). Each treatment comparison p-value is to be tested at the 0.05 alpha level.

Observed and change from Baseline values are to be summarised by descriptive statistics (n, mean, SD, median, minimum and maximum) for each annual Allergy Assessment Period and treatment arm.

The analyses are to be repeated for the mITT population.

#### 13.2.2.4. Rhinoconjunctivitis Quality of Life Questionnaire (RQLQ) Score

The LS mean difference in RQLQ total score between treatment arms, along with 95% two-sided CIs and p-value are to be estimated using the same ANCOVA as for the primary efficacy variable as described in [Section 13.1.2: Primary Analysis of Primary Efficacy Variable](#) and presented in a similar manner, excluding the ratio of LS means and 95% Fieller's CI.

Additionally, the LS mean and 95% CI for the RQLQ at the CP007 study endpoint of PAC3 is to be calculated for the CP007A FAS subjects using the same ANCOVA. The LS mean and 95% CI is to be presented by treatment arm.

The RQLQ analysis is not to utilize the Bonferroni-Holm procedure to assess each of the two treatment comparisons (two courses of Cat-PAD vs. Placebo and one course of Cat-PAD vs. Placebo). Each treatment comparison p-value is to be tested at the 0.05 alpha level. Observed and change from Baseline values are to be summarised by descriptive statistics (n, mean, SD, median, minimum and maximum) for each annual Allergy Assessment Period and treatment arm, for the total score as well as each domain.

The analyses are to be repeated for the mITT population.

---

Document: CP007A SAP.docx

Author: [name]

Version Number:

V 2.0

Version Date:

23 Feb 2017

Template No: CS\_TP\_BS016 – Revision 3

Reference: CS\_WI\_BS005

Effective Date: 01May2012

Copyright © 2012 Quintiles Transnational Corp. All rights reserved.

The contents of this document are confidential and proprietary to Quintiles Transnational Corp. Unauthorized use, disclosure or reproduction is strictly prohibited.

### 13.2.2.5. Asthma Evaluations

- Mean Asthma Symptom Score (ASS)

Mean ASS is to be summarised separately for:

- Subjects with asthma
- All subjects (including subjects with asthma)

Observed and change from Baseline values are to be summarised by descriptive statistics (n, mean, SD, median, minimum and maximum) for each annual Allergy Assessment Period and treatment arm.

- Asthma Onset and Progression

The number and percentage of subjects that answer “Yes” or “No” to each asthma progression question are to be presented for each monthly assessment and treatment arm.

The denominator for the percentage of subjects diagnosed with asthma as recorded at each month’s asthma assessment is the total number of subjects in the population treatment arm with data available.

The denominator for the percentage of subjects whose doctor has prescribed stronger medicine and whose symptoms have been significantly worse in the past month is the total number of subjects in the population treatment arm that are diagnosed with asthma at each relevant month’s asthma assessment.

The number and percentage of subjects that have been diagnosed with asthma in the past year are to be presented for each annual assessment and treatment arm.

The percentage of subjects diagnosed with asthma in the past year are to be compared between the two active treatments and Placebo by using a logistic regression model with pooled site, treatment as main effect and age group (adolescents, adults), gender, asthma status (present, absent) and Baseline CS as covariates. Odds ratios with 95% CI and p-values are to be presented for the individual treatment comparisons vs. Placebo.

The analysis is to be repeated for the mITT population.

---

Document: CP007A SAP.docx

Author: [name]

Version Number:

V 2.0

Version Date:

23 Feb 2017

Template No: CS\_TP\_BS016 – Revision 3

Reference: CS\_WI\_BS005

Effective Date: 01May2012

Copyright © 2012 Quintiles Transnational Corp. All rights reserved.

The contents of this document are confidential and proprietary to Quintiles Transnational Corp. Unauthorized use, disclosure or reproduction is strictly prohibited.

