### 5.2. FULL ANALYSIS SET [FAS]

The Full Analysis Set (FAS) will consist of all subjects who are consented into the study and have at least one day of symptom scores and rescue medication use recorded during the annual Allergy Evaluation Period of CP007A. Subjects are to be listed and summarised by the treatment they were randomised to in study CP007. The FAS population is to be re-assessed for each analysis year to account for subject drop-outs during each year.

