## 7. STATISTICAL CONSIDERATIONS

### 7.1. ADJUSTMENTS FOR COVARIATES AND FACTORS TO BE INCLUDED IN ANALYSES

The following covariates and factors are used in the analyses. For details of their inclusion in the models, see the specific analysis section.

- Pooled site [Pooled Site 01,...,Pooled Site xx]
- Age group [Adolescents/Adults], assigned based on subject's age as entered on the Enrolment Visit CRF for CP007A
- Gender [Male/Female], as collected at the CP007 Screening visit
- Asthma status [Present/Absent], as collected at the CP007 Screening visit
- Baseline score [Represents the Baseline value of the relevant score being analysed], where Baseline is defined as in [Section 6.2](#): Baseline.

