### 7.2. MULTICENTRE STUDIES

This study is to be conducted by multiple Investigators at multiple centres internationally.

If a centre has less than five subjects, pooling with other centre(s) is performed based on geographical region, and is to be completed and agreed with Circassia prior to unblinding.

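### The SAP's two asthma analyses do not use the populations their objectives name: the onset model includes subjects who already have asthma, and the progression denominator is whoever reports a diagnosis that month

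*SAP*

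**What the plan says.** **Objectives.** Protocol 2.2 and SAP 2.2 set two secondary asthma objectives: the effect on onset, and the effect on progression in subjects who entered CP007 with GINA 1 asthma. Protocol 7.4.2.2.6 promises separate evaluations of progression and of the number of subjects who develop asthma. Protocol 3.2.3, however, lists progression among the exploratory endpoints.

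**Onset analysis.** At the start of each annual period, subjects state whether "they have been diagnosed with asthma during the last year" (SAP 13.2.1.5). SAP 13.2.2.5 then says: "The percentage of subjects diagnosed with asthma in the past year are to be compared between the two active treatments and Placebo", using "a logistic regression model with pooled site, treatment as main effect and age group (adolescents, adults), gender, asthma status (present, absent"), with Baseline CS as a further covariate. SAP 7.1 gives the source of the status term: "Asthma status [Present/Absent], as collected at the CP007 Screening visit". SAP 13.2.2 fixes the population: "The secondary efficacy analysis is to be performed for the FAS". The analysis is repeated in the mITT. The FAS is made up of consented subjects who "have at least one day of symptom scores and rescue medication use recorded during the annual Allergy Evaluation Period of CP007A" (SAP 5.2).

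**Progression analysis.** Progression is reported as monthly Yes/No counts. For stronger medicine and for worse symptoms, the denominator is the "total number of subjects in the population treatment arm that are diagnosed with asthma at each relevant" month's assessment. No comparison between arms is planned.

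**The concern.** Onset can occur only in people without the disease. An onset percentage whose denominator includes existing asthmatics is not a rate in people at risk. The odds ratio also comes to depend on how existing asthmatics read a question that is meant for new cases.

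The progression objective names a group fixed before treatment. The SAP's denominator is formed after randomisation: it gains new cases and loses anyone who answers No that month. If treatment affects onset, which is the companion objective, the arms' denominators will differ because of treatment.

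At stake are the odds ratios, confidence intervals and p-values planned for one secondary objective, and the descriptive percentages for the other.

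**Working it through.** The plan states no asthma rate, so it has no figure of its own to reproduce. The first and third checks compare texts. The others use assumed rates.

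**1. Who is in the onset model.**
- The FAS definition has no asthma criterion, and the mITT is a subset of the FAS.
- The model carries asthma status. That term would be constant if only subjects without asthma were analysed, so existing asthmatics are included.
- The diary-based asthma classification in SAP 13.2.1.5 follows the asthma symptom score and does not restrict the onset model.
- SAP 6.4 says each analysis section specifies its denominator. SAP 13.2.2.5 does so for the monthly percentages but not for the annual one.

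**2. Effect on the onset result.** Assumptions: yearly onset in at-risk subjects of 3.0% on placebo and 1.5% on each active regimen; a share f of the FAS asthmatic at CP007 Screening (0.4, range 0.2 to 0.6); a share q of these answering Yes, equal across arms.

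True odds ratio = (0.015/0.985)/(0.030/0.970) = 0.49.

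Reported percentage = (1 − f) × onset + f × q. With q = 0 and f = 0.4 this is 0.6 × 3.0% = 1.8% against 0.6 × 1.5% = 0.9%. At f = 0.2 it is 2.4% against 1.2%, and at f = 0.6 it is 1.2% against 0.6%.

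Odds ratio from a logistic model with treatment and asthma status, fitted to expected counts:

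| q | f = 0.2 | f = 0.4 | f = 0.6 |
|---|---|---|---|
| 0 | 0.49 | 0.49 | 0.49 |
| 0.2% | 0.50 | 0.51 | 0.54 |
| 1% | 0.53 | 0.59 | 0.66 |
| 5% | 0.64 | 0.76 | 0.85 |

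Hand check at q = 1%, f = 0.4: the percentages are 2.2% and 1.3%, and the crude odds ratio is (0.013/0.987)/(0.022/0.978) = 0.59. At q = 0 no asthmatic has an event, so the status coefficient diverges.

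**3. Who is in the progression denominator.** In the SAP, GINA appears only in the abbreviation list and in the objective. No baseline variable, subgroup or analysis uses it. By contrast, SAP 13.3.2.2 limits the exploratory ACQ summary to a group fixed at CP007 Screening.

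**4. Size of the progression distortion.** Under the same onset rates, the new cases by the end of Year 4 are n = (1 − f)(1 − (1 − p)^4), and their share of the denominator is n/(f + n).
- Placebo at f = 0.4: n = 0.6 × 0.1147 = 0.0688; share 0.0688/0.4688 = 14.7%.
- Active at f = 0.4: n = 0.6 × 0.0587 = 0.0352; share 0.0352/0.4352 = 8.1%.

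Suppose 20% of existing asthmatics progress in every arm, and 5% to 50% of new cases do. The false active-minus-placebo difference is (8.1% − 14.7%) × (0.05 − 0.20) = +1.0 point, to (8.1% − 14.7%) × (0.50 − 0.20) = −2.0 points. At f = 0.2 it is +1.9 to −3.7 points.

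**5. Diagnoses made after randomisation.** Among subjects with asthma Absent at Screening, some will have been diagnosed before the year analysed and are no longer at risk. Taking CP007 as about one year, leaving that year's diagnoses in gives (0.014775/0.985225)/(0.0291/0.9709) = 0.50. Leaving in four years' diagnoses (11.5% against 5.9%) gives 0.525 at Year 4. Both shifts from 0.49 are negligible.

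**6. Handling No months.** Assume 20% progress when diagnosed, and that 10% of months in one arm and 20% in another are answered No to having asthma. Counting those months as not progressed gives 0.20 × 0.90 = 18.0% against 0.20 × 0.80 = 16.0%, a false difference of 2 points. Excluding them gives 20% in both.

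**The case against.** **The onset item already targets new cases.** It asks about the last year. If existing asthmatics answer it as worded, they answer No and the odds ratio is unharmed. The shift to 0.76 needs 5% of them to answer Yes each year, more than the assumed placebo onset. This stands. A reader might infer that the planned odds ratio is biased by design; the documents do not support that, because they give no rate of Yes answers. What remains in every case is the diluted percentage, the unstated denominator and the uninformative status term.

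**Sparse events.** A reader might also infer that the model must have more site terms than events, because SAP 7.2 says: "If a centre has less than five subjects, pooling with other centre(s) is performed based on geographical region". The documents give neither an onset rate nor a pooled-site count, so this cannot be asserted. With 40% asthmatic there are 78, 160 and 281 at-risk subjects per arm, from 130 and 266 (Protocol 7.2, used only as example sizes) and 469 = 1408/3 (SAP 3.1, an upper bound that assumes equal allocation). Expected events over three arms are n × (placebo rate + 2 × active rate): 4.7, 9.6 and 16.9 at 3.0%/1.5%, but 15.6, 32.0 and 56.2 at 10%/5%. Sparsity is a contingency to plan for.

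**Progression is descriptive, and CP007 may have admitted only GINA 1 asthma.** CP007's eligibility criteria are not in these documents. If that was the rule, the gap narrows to new cases and No months. This stands, so a reader should not infer that the table mixes asthma severities from CP007 entry. The objective is nevertheless an effect of treatment in a named group, and the plan offers neither that group nor a comparison.

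**Conclusion.** The mismatch between objectives and analysis populations is established by the text. The harm is conditional. For onset, the percentages are diluted by the asthmatic fraction if existing asthmatics all answer No, and the odds ratio moves towards 1 only if some answer Yes. For progression, the distortion is about 1 to 2 points at 40% asthmatic and up to 3.7 points at 20%. Every rate behind these figures is an assumption.

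SAP 13.1.2 ties study success to the primary variable alone, so only secondary claims are affected. The severity is minor to low should-fix.

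**What to change.** 1. **Onset.** Fit the model and report the annual percentage in subjects with asthma Absent at CP007 Screening. State that denominator, drop the asthma-status covariate and show event counts per arm. Keep diagnoses made after CP007 randomisation in the main analysis: removing them would create a post-randomisation group to correct a negligible shift, so do it at most as a sensitivity analysis. State in advance that if events are few relative to the pooled-site terms, pooled site is dropped and Firth or exact estimation is used.
2. **Progression.** Report it in a fixed pre-treatment group: CP007 GINA 1 subjects if that field is held, otherwise asthma Present at CP007 Screening, as the ACQ summary does. Exclude No months in the main summary and count them as not progressed only as a sensitivity analysis. Give each regimen's difference from placebo with a 95% CI per analysis year. Keep the current monthly table as supportive.
3. **Status.** Reconcile Protocol 2.2 and SAP 2.2 with Protocol 3.2.3 on whether progression is secondary or exploratory.

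**Cost.** SAP wording, one model and two tables. Screening asthma status is already held; whether the GINA step is held must be checked. The restricted sets have fewer subjects and wider intervals. Onset stays imprecise if events are few: at 3.0%/1.5%, the simulated median 95% CI from a treatment-only Firth model is 0.08–4.59, 0.12–2.44 and 0.16–1.65 with 78, 160 and 281 at-risk subjects per arm.

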2.2 Secondary Objectives

- To evaluate the continued safety and tolerability of Cat-PAD for up to five years after the administration of treatment.
- To evaluate the effect of Cat-PAD on Rhinoconjunctivitis Quality-of-Life Questionnaire (RQLQ) for up to five years after the administration of treatment.
- To evaluate the effect of Cat-PAD on the onset of asthma for up to five years after the administration of treatment.
- To evaluate the effect of Cat-PAD on asthma progression in subjects previously enrolled in CP007 with GINA 1 asthma for up to five years after the administration of treatment.

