7.4.2.2.6 Asthma

An evaluation of asthma progression and the number of subjects developing asthma during the study will be performed in separate analyses.

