### 2.2. SECONDARY OBJECTIVES

The secondary objectives are:

- To evaluate the continued safety and tolerability of Cat-PAD for up to 5 years after the administration of treatment.
- To evaluate the effect of Cat-PAD on the Rhinoconjunctivitis Quality of Life Questionnaire (RQLQ) for up to 5 years after the administration of treatment.
- To evaluate the effect of Cat-PAD on the onset of asthma for up to 5 years after the administration of treatment.
- To evaluate the effect of Cat-PAD on asthma progression in subjects previously enrolled in CP007 with Global Initiative for Asthma (GINA) 1 asthma for up to 5 years after the administration of treatment.

---

Document: CP007A SAP.docx

Author: [name]

Version Number:

V 2.0

Version Date:

23 Feb 2017

Template No: CS\_TP\_BS016 – Revision 3

Reference: CS\_WI\_BS005

Effective Date: 01May2012

Copyright © 2012 Quintiles Transnational Corp. All rights reserved.

The contents of this document are confidential and proprietary to Quintiles Transnational Corp. Unauthorized use, disclosure or reproduction is strictly prohibited.

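### The only between-arm test of asthma onset is a one-year snapshot at each annual assessment, so no planned comparison accumulates onsets over follow-up

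*SAP*

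**What the plan says.** **Objective.** Protocol 2.2 reads "To evaluate the effect of Cat-PAD on the onset of asthma for up to five years after the administration of treatment", and SAP 2.2 repeats it. Protocol 7.4.2.2.6 covers progression and onset together; on onset it says "the number of subjects developing asthma during the study will be performed in separate analyses". That is a count over the whole study.

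**Variable.** SAP 13.2.1.5 defines one past-year item. Its timing is given as "at the start of each annual Allergy Assessment Period subjects will indicate whether", and its look-back window as "they have been diagnosed with asthma during the last year". The same section lists a monthly diary question on whether the subject is diagnosed with asthma, which records current status.

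**Analysis.** SAP 13.2.2.5 first plans a descriptive count: "subjects that have been diagnosed with asthma in the past year are to be presented for each annual assessment and treatment arm". It then gives the only treatment comparison: "The percentage of subjects diagnosed with asthma in the past year are to be compared between the two active treatments and Placebo", by logistic regression with odds ratios for each active arm against placebo. The monthly answers are tabulated by month and arm without a test.

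**Population and data cut.** SAP 13.2.2 puts secondary efficacy in the FAS. Under SAP 5.2 a subject needs at least one diary day in that year's annual period to belong to it, and "The FAS population is to be re-assessed for each analysis year to account for subject drop-outs during each year". SAP 4.1 takes each analysis from that year's diary binder. SAP 4 and 7.4 run Years 2 to 4 only after a positive outcome in the earlier years.

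**The concern.** The protocol asks how many subjects develop asthma over follow-up. The SAP asks, separately each year, how many of those still supplying annual diaries report a diagnosis in the preceding year. A subject diagnosed in Year 1 is therefore a non-event in the Year 4 model, and nothing combines the years.

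Two smaller gaps follow from the same rule. A subject who reports a diagnosis in a monthly diary and withdraws before the annual period is outside that year's FAS. A subject who skips one annual diary and returns is next asked only about the last year, so an onset in the skipped year enters no tested comparison. SAP 7.3 does not help: it refers missing efficacy data to the Combined Score imputation rules, which cannot supply a missing asthma answer.

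At stake is whether a secondary objective can be answered. Onset is likely to be infrequent, and an effect lasting several years would be split over separate models with few events each.

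**Working it through.** **The plan's own figures.** The documents give no onset rate and no power for onset. The only powered figures (Protocol 7.2) concern the Combined Score: difference 0.525, SD 1.29, two-sided alpha 0.025. They reproduce as 99.3% power at 266 per arm and 85.1% at 130 per arm, but say nothing about onset.

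**Reading check.** The SAP does not name the source field for the past-year percentage. The annual question in 13.2.1.5 is the only past-year item defined, so I take it as the source. That each model uses one year's answers follows from the per-assessment presentation in 13.2.2.5 and the one-binder data cut in 4.1.

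**Illustration (assumed inputs).** N = 200 at-risk subjects per arm, onset h = 2% per year, withdrawal w = 10% per year, annual diary at month 12k, monthly diaries complete until withdrawal, no annual diary skipped.

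- Onsets in the Year k past-year model: N × (1−w)^k × (1−h)^(k−1) × h. For Year 1, 200 × 0.90 × 0.02 = 3.60. For Year 4, 200 × 0.90^4 × 0.98^3 × 0.02 = 2.47.
- Cumulative first onsets to Year k: monthly onset is 1 − 0.98^(1/12) = 0.0016821 and monthly withdrawal is 1 − 0.90^(1/12) = 0.0087416. The monthly chance of staying in the study and free of asthma is 0.989591, or 0.98 × 0.90 = 0.882 per year. The count is 200 × 0.0016821 × (1 − 0.882^k) / (1 − 0.989591) = 32.32 × (1 − 0.882^k).
- Approximate SE of the log ratio: √(2 / onsets per arm).

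| Annual cut | Past-year onsets per arm | SE | Cumulative onsets per arm | SE |
|---|---|---|---|---|
| 1 | 3.60 | 0.75 | 3.81 | 0.72 |
| 2 | 3.18 | 0.79 | 7.18 | 0.53 |
| 3 | 2.80 | 0.85 | 10.14 | 0.44 |
| 4 | 2.47 | 0.90 | 12.76 | 0.40 |

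**Direct loss around withdrawal.** The four annual counts sum to 12.05, so 12.76 − 12.05 = 0.71 onsets per arm (5.6%) enter no annual model. Over 1% to 3% onset and 5% to 15% withdrawal per year, the loss is 2.8% to 8.6%, cumulative onsets are 5.8 to 20.8 per arm, and the Year 4 model holds 1.0 to 4.5.

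**Second set of assumptions.** Take 266 per arm, all treated as asthma-free, falling to 130 over four years: 1 − (130/266)^(1/4) = 16.4% withdrawal per year. At 2% onset there are 14.9 cumulative onsets per arm. The direct loss is 9.4% with no skipped annual diary, 13.9% with 5% skipped and 18.4% with 10% skipped. With 5% skipped, power at two-sided 0.05 to detect 2% against 1% per year is 35% cumulatively, 13% for Year 1 alone and 9% for Year 4 alone.

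**The case against.** - **Nearly all onsets enter some annual model.** In the main illustration that is 12.05 of 12.76, and pooling them would give an SE of √(2/12.05) = 0.41 against 0.40. This stands. A reader might infer from 12.8 against 2.5 that most events are discarded, but the gap arises because the years are never combined. The SAP plans no pooling, so the point survives in that form.
- **Later years are conditional.** At Year 1, the only assured analysis, the two counts almost coincide (3.60 and 3.81). This stands: the gain appears only at Years 2 to 4, if they are run.
- **Onsets are visible elsewhere.** The monthly table would still show a returning subject as diagnosed. New asthma reported at a visit can also be an adverse event (Protocol 6.4.1), and adverse events are cumulative (SAP 4.1), cover all subjects (SAP 5.4) and are shown by Preferred Term (SAP 14.1.1). So the events need not be invisible. However, the monthly table is FAS prevalence mixed with existing asthma, neither output is a treatment comparison, and neither gives first onsets among subjects at risk.
- **Bias is hypothetical.** A reader might infer a biased odds ratio. That needs withdrawal after onset to differ by arm, and the documents give no evidence of it. Censoring at the last diary is open to the same problem.
- **Low priority.** Onset is a secondary objective but is absent from the secondary endpoint list (Protocol 3.2.2), and it has no power statement. This limits the severity. It does not reconcile the SAP with Protocol 7.4.2.2.6.

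**Conclusion.** The point holds as a mismatch between objective and analysis. The protocol calls for onsets over the study, and the SAP tests only past-year percentages in yearly analysis sets. Under the main assumptions a single annual model has an SE of 0.75 to 0.90, against 0.40 for the four-year cumulative count.

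The size rests on assumed onset, withdrawal and at-risk numbers, and on later analyses taking place. Loss of onsets recorded before withdrawal is secondary, about 3% to 9% over 5% to 15% withdrawal per year, and more if annual diaries are skipped. The documents do not support a claim that most onsets are lost or that the comparison is biased. Even the cumulative test would have modest power, but it estimates what the protocol describes. The change should be made, though it does not affect the primary analysis.

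**What to change.** In SAP 13.2.2.5, make the onset comparison cumulative at each annual cut that is performed:

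- **At-risk set:** all enrolled subjects without asthma at CP007 screening, whether or not they are in that year's FAS. This must be stated, because the monthly question records current status and a first Yes is otherwise prevalence.
- **Event:** first reported diagnosis in any monthly or annual diary to date, censored at the last completed monthly diary.
- **Presentation:** cumulative incidence by arm, with a time-to-first-diagnosis or discrete-time comparison of each active arm with placebo.
- **Consequential edits:** exempt this endpoint from the FAS rule in SAP 13.2.2, and amend SAP 4.1 so that diary data are linked across years. Keep the annual past-year percentage as description.

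**Cost.** No new data or visits are needed, but this is more than one derived variable: it needs a new analysis set and linkage across yearly database snapshots. Onset remains self-reported and dated only to the month, and censoring may still be informative. A Yes in the first monthly diary may reflect a diagnosis made during CP007, so the SAP should say how it is dated.
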